4.1.2. Phase 2 – Dose Expansion

The Phase 2 dose expansion cohorts will begin when the MTD or PAD of epacadostat has been determined in Phase 1 for the respective treatment group. This portion of the study will evaluate the efficacy of the MTD or PAD of epacadostat and will further evaluate the safety, [REDACTED] of the combinations.

Treatment Group A will enroll 2 expansion cohorts in parallel:

- **Cohort A1:** Approximately 35 subjects with unresectable or metastatic MEL who have not received prior systemic treatment for advanced or metastatic disease. Serial pretreatment and on-treatment biopsies are required for all subjects enrolled, if clinically feasible.
- **Cohort A2:** Approximately 35 subjects with advanced or metastatic NSCLC without known driver mutations (including EGFR, BRAF, ALK, and ROS1) who have received no more than 1 prior line of therapy for advanced or metastatic disease. Serial pretreatment and on-treatment biopsies are required for all subjects enrolled, if clinically feasible.

Treatment Group B will enroll 1 expansion cohort:

- **Cohort B1:** Approximately 35 subjects with recurrent or metastatic SCCHN who have received no more than 1 prior line of platinum-based chemotherapy for recurrent or metastatic disease. Serial pretreatment and on-treatment biopsies are required for all subjects enrolled, if clinically feasible.

Enrollment into the Phase 2 expansion cohorts will begin when the MTD or PAD of epacadostat for the corresponding treatment group in Phase 1 has been determined; however, priority will be given to any open dose-escalation cohorts in Phase 1.

In Phase 2 of the study, toxicities will continue to be monitored. If the cumulative incidence of \geq Grade 3 immune-related AEs is $> 40\%$ after a cumulative minimum of 10 subjects have been enrolled into the expansion cohorts within each treatment group, further enrollment in those expansions will be interrupted until the sponsor, investigators, and regulatory authorities (if applicable) determine the appropriate course of action. If an expansion cohort in a particular treatment group is discontinued because of toxicity, a new expansion may be initiated at a previously tested lower dose level of epacadostat.

The sponsor may elect to prioritize enrollment to specific treatment groups or expansion cohorts based on emerging safety or efficacy data in collaboration with investigational sites.

4.2. Measures Taken to Avoid Bias

This is an open-label study. Assessment of safety using CTCAE v4.03 and efficacy using RECIST v1.1 [REDACTED] are objective measurements, and only comparisons to pretreatment conditions will be made.

4.3. Number of Subjects

4.3.1. Planned Number of Subjects

Approximately 141 subjects may be enrolled into the study at approximately 15 to 20 sites.

Treatment Group A:

- **Phase 1:** Approximately 18 subjects.
- **Phase 2:** Cohort A1 – approximately 35 subjects
Cohort A2 – approximately 35 subjects

Treatment Group B:

- **Phase 1:** Approximately 18 subjects.
- **Phase 2:** Cohort B1 – approximately 35 subjects.

4.3.2. Replacement of Subjects

Subjects may be replaced for any of the following reasons:

- In Phase 1, any subject who withdraws from treatment before the completion of the DLT observation period for any reason other than a DLT (ie, is not evaluable for DLTs; see Section 5.4.2) or who does not have the required exposure to the study drugs during the DLT evaluation period, may be replaced to ensure a minimum number of evaluable subjects.
- Subjects who do not meet the eligibility requirements of the study may be replaced.

Subjects who meet any of the criteria for replacement may remain on study for evaluation as outlined in Section 9.1 and Section 9.2.

4.4. Duration of Treatment and Subject Participation

After signing the ICF, screening assessments may be completed over a period of up to 28 days. Each subject enrolled in the study may continue to receive study treatment in continuous 14-day cycles for up to 2 years, as long as they are deriving benefit and have not met any of the Protocol-defined conditions for treatment withdrawal (see Section 5.5.1). If the subject discontinues study treatment, the treatment period will end and the subject will enter the safety follow-up period (see Section 6.4). Study participation, including post-treatment safety follow-up, is expected to average approximately 12 to 18 months per individual subject.

4.5. Overall Study Duration

The study begins when the first subject signs the ICF. The end of the study will occur when all subjects have discontinued treatment and the last follow-up visit has been performed.

If there have been ≤ 5 subjects on study for more than 6 months, a database lock of the study may occur to allow the analysis of the study data. Any remaining subjects may continue to receive study treatment and be seen by the investigator per usual standard of care for this population. The investigator will be expected to monitor for and report any SAEs, AEs of

special interest, and pregnancies, as detailed in Section 8. The remaining subjects are considered to be on study until a discontinuation criterion is met and written notification is provided to the sponsor.

4.6. Study Termination

The investigator retains the right to terminate study participation at any time according to the terms specified in the study contract. The investigator is to notify the IRB/IEC in writing of the study's completion or early termination, send a copy of the notification to the sponsor or sponsor's designee, and retain 1 copy for the site study regulatory file.

The sponsor may terminate the study electively, if required by regulatory decision, or upon review of emerging data. If the study is terminated prematurely, the sponsor will notify the investigators, the IRBs and IECs, and regulatory bodies of the decision and reason for termination of the study.

5. TREATMENT

5.1. Treatment Assignment

5.1.1. Subject Numbering and Treatment Assignment

Each subject will be identified in the study by a subject ID number, which is a combination of the site ID and subject number. Site staff should contact the IRT to obtain the subject ID number during screening. This subject ID number will be maintained throughout the study and will not be reassigned. Subjects who fail screening and are repeating the screening process due to a change in eligibility status will be assigned a new subject ID number. For subjects who signed an ICF but are not treated, refer to the eCRF Completion Guidelines for instructions on which eCRFs to complete.

Site staff will contact the IRT to enroll the subject and obtain the initial assignment for the relevant treatments. The investigator or designee will select the assigned treatments from the stock that correspond to the number provided by the IRT, record the unique identifiers in the eCRF, and dispense the treatment to the subject. All subsequent dispensing of relevant treatments should follow this process. Full details will be provided in the IRT manual.

If a subject is mistakenly dispensed a bottle of study drug that is not the bottle assigned by the IRT, then the IRT help desk must be notified immediately. The reason for the misallocation of the study drug must be documented by the study site.

5.1.2. Randomization and Blinding

This is an open-label nonrandomized study; therefore, randomization and blinding do not apply.

5.2. Study Drugs

5.2.1. Epacadostat

For all subjects, epacadostat will be self-administered beginning on Cycle 1 Day 1 and continuously thereafter. Doses will be taken BID, in the morning and evening, approximately 12 hours apart without regard to food. If a dose is missed by more than 4 hours, then that dose should be skipped and the next dose should be taken at the next scheduled timepoint.

On Cycle 1 Day 1, Cycle 1 Day 8, and Cycle 2 Day 1, the morning dose of epacadostat will be administered at the study site, as these study visits coincide [REDACTED]. On visit days when nivolumab and ipilimumab (Treatment Group A) or nivolumab and lirilumab (Treatment Group B) are administered, epacadostat should be taken before the start of any infusions.

Note: Subjects who are ongoing on study treatment as of the date of Amendment 2 may discontinue epacadostat at the discretion of the treating investigator (see Section 1.7).

5.2.1.1. Supply, Packaging, and Labeling

Epacadostat will be available as 25 mg and 100 mg tablets packaged in high-density polyethylene bottles. In Phase 1, subjects will receive epacadostat according to dose level assignment (Table 3). In Phase 2, all subjects will receive epacadostat at the MTD or PAD identified in Phase 1. All tablet excipients comply with the requirements of the applicable compendial monographs (Ph. Eur., USP/NF; refer to the [epacadostat IB](#)).

All Incyte investigational product labels will be in the local language and will comply with the legal requirements of each country.

5.2.1.2. Storage

Clinical supplies must be stored as described in the [epacadostat IB](#).

5.2.2. Nivolumab

5.2.2.1. Description and Administration

Subjects will receive nivolumab 240 mg as a 30-minute IV infusion (\pm 5 minutes) on Day 1 of each 14-day cycle, starting at Cycle 1 Day 1. Intrasubject dose escalation of nivolumab is not permitted. Nivolumab will be administered after epacadostat. Sites are instructed to wait at least 30 minutes after the nivolumab infusion is completed before administering subsequent infusions of ipilimumab (Treatment Group A) or lirilumab (Treatment Group B).

Details on the preparation and administration are provided in the Pharmacy Manual.

5.2.2.2. Supply, Packaging, and Labeling

The investigator will take responsibility for and shall take all steps to maintain appropriate records and ensure appropriate supply, storage, handling, distribution, and usage of nivolumab in accordance with the protocol and any applicable laws and regulations. Nivolumab clinical supplies will be provided by BMS and will be labeled in accordance with local regulatory requirements.

The nivolumab product description is provided in [Table 4](#). Refer to the [nivolumab IB](#) for additional details.

Table 4: Nivolumab Product Description

Product Description and Regimen Form	Potency	Primary Packaging Volume/ Label Type	Secondary Packaging/ Label Type	Appearance	Storage Conditions
Nivolumab (BMS-936558) solution for injection.	100 mg (10 mg/mL)	10 mg/mL vial/open-label	5 vials per carton/ open-label	Clear to opalescent colorless to pale yellow liquid, may contain particles.	2°C to 8°C. Protect from light and freezing.

5.2.3. Ipilimumab

5.2.3.1. Description and Administration

Subjects in Treatment Group A will receive ipilimumab 1 mg/kg as a 30-minute IV infusion (\pm 5 minutes) starting at Cycle 1 Day 1 and Q6W thereafter on Day 1 of every third treatment cycle (eg, Cycle 4, Cycle 7, etc). Intrasubject dose escalation of ipilimumab is not permitted. When administered on the same day, ipilimumab will be administered at least 30 minutes after the completion of the nivolumab infusion.

Details on the preparation and administration are provided in the Pharmacy Manual.

5.2.3.2. Supply, Packaging, and Labeling

The investigator will take responsibility for and shall take all steps to maintain appropriate records and ensure appropriate supply, storage, handling, distribution, and usage of ipilimumab in accordance with the protocol and any applicable laws and regulations. Ipilimumab clinical supplies will be provided by BMS and will be labeled in accordance with local regulatory requirements.

The ipilimumab product description is provided in [Table 5](#). Refer to the [ipilimumab IB](#) for additional details.

Table 5: Ipilimumab Product Description

Product Description and Regimen Form	Potency	Primary Packaging Volume/ Label Type	Secondary Packaging/ Label Type	Appearance	Storage Conditions
Ipilimumab (BMS-734016) solution for injection.	200 mg/40 mL (5 mg/mL)	5 mg/mL vial/open-label	4 vials per carton/ open-label	Clear to slightly opalescent, colorless to pale yellow liquid, may contain particles.	2°C to 8°C. Protect from light and freezing.

5.2.4. Lirilumab

5.2.4.1. Description and Administration

Subjects in Treatment Group B will receive lirilumab 240 mg as a 60-minute IV infusion (\pm 5 minutes) starting at Cycle 1 Day 1 and Q4W thereafter on Day 1 of every other treatment cycle (eg, Cycle 3, Cycle 5, etc). Intrasubject dose escalation of lirilumab is not permitted. When administered on the same day, lirilumab will be administered at least 30 minutes after the completion of the nivolumab infusion.

Details on the preparation and administration are provided in the Pharmacy Manual.

5.2.4.2. Supply, Packaging, and Labeling

The investigator will take responsibility for and shall take all steps to maintain appropriate records and ensure appropriate supply, storage, handling, distribution, and usage of lirilumab in accordance with the protocol and any applicable laws and regulations. Lirilumab clinical supplies will be provided by BMS and will be labeled in accordance with local regulatory requirements.

The lirilumab product description is provided in [Table 6](#). Refer to the [lirilumab IB](#) for additional details.

Table 6: Lirilumab Product Description

Product Description and Regimen Form	Potency	Primary Packaging Volume/ Label Type	Secondary Packaging/ Label Type	Appearance	Storage Conditions
Lirilumab (BMS-986015) solution for injection.	100 mg/10 mL (10 mg/mL)	10 mg/mL vial/open-label	6 vials per carton/ open-label	Clear to opalescent, colorless liquid, may contain few particles.	2°C to 8°C. Protect from light and freezing.

5.3. Treatment Compliance

Epacadostat is an oral medication, and compliance will be calculated by the sponsor based on the drug accountability documented by the site staff and monitored by the sponsor/designee (tablet counts). The objective is 100% compliance, and site staff should evaluate compliance at each visit and take appropriate steps to optimize compliance.

Nivolumab, ipilimumab, and lirilumab are administered as an IV infusion by site personnel. Receipt of infusions will be documented by the site staff and monitored by the sponsor/designee.

5.4. Treatment Interruptions and Adjustments

5.4.1. Dose Modifications

Modifications to epacadostat dosing are planned for the Phase 1 dose-escalation cohorts (see Section 4.1.1). Dose modifications in the form of interruption or discontinuation for any of the study treatment components (epacadostat, nivolumab, ipilimumab [Treatment Group A] or lirilumab [Treatment Group B]) may also be needed for individual subjects in the event of a DLT

or AE (related or unrelated to treatment). Intrasubject dose escalation for epacadostat, nivolumab, ipilimumab, or lirilumab is not permitted.

5.4.2. Dose-Limiting Toxicity and Determination of Maximum Tolerated Dose

A DLT will be defined as the occurrence of any of the toxicities in [Table 7](#) occurring from Cycle 1 Day 1 up to and including Day 42 for Treatment Groups A and B in Phase 1, except those with a clear alternative explanation (eg, disease progression) or transient (≤ 72 hours) abnormal laboratory values without associated clinically significant signs or symptoms based on investigator determination. Immune-related AEs of Grade 3 that improve to Grade 1 or lower within 14 days after the initiation of supportive care or corticosteroid therapy may be deemed a non-DLT. All DLTs will be assessed by the investigator using CTCAE v4.03 criteria.

To be evaluable for tolerability, subjects in Treatment Group A must receive at least 75% of planned epacadostat doses (63/84) at the specified dose level, 3 doses of nivolumab, and 1 dose of ipilimumab, or subjects must experience a DLT during the DLT observation period. Subjects in Treatment Group B must receive at least 75% of planned epacadostat doses (63/84) at the specified dose level, 2 doses of nivolumab, and 2 doses of lirilumab, or subjects must experience a DLT during the DLT observation period.

Individual subject dose reductions may be made based on events observed at any time during treatment with study drug; however, for the purposes of dose cohort escalation/de-escalation, expanding a dose cohort, and determining the MTD of epacadostat, decisions will be made based on events that are observed from the first day of study drug administration through the above-defined DLT observation period for each treatment group. A lower MTD may subsequently be determined based on relevant toxicities that become evident after the DLT observation period.

Table 7: Definition of Dose-Limiting Toxicity

Toxicity
Nonhematologic

 • Any liver function abnormalities that meet the definition of Hy's law^a • Any grade encephalopathy. • ≥ Grade 2 ocular irAEs. • Grade 4 irAEs will be considered a DLT regardless of duration. • Any ≥ Grade 3 nonhematologic toxicity EXCEPT: 
 – Transient (≤ 72 hours) abnormal laboratory values without associated clinically significant signs or symptoms. – Nausea, vomiting, and diarrhea adequately controlled with medical therapy within 48 hours. – Grade 3 rash in the absence of desquamation, with no mucosal involvement, that does not require systemic steroids and that resolves to Grade 1 in ≤ 14 days. – ≥ Grade 3 changes in amylase and lipase that is not associated with symptoms or clinical manifestations of pancreatitis. – Asymptomatic changes in lipid profiles. – Singular or nonfasting elevations in blood glucose (ie, blood glucose excursions will be considered toxicities if fasting blood glucose is elevated on 2 separate occasions). – Grade 3 irAE that improves to ≤ Grade 1 in ≤ 14 days by appropriate care or with corticosteroid therapy. – Grade 3 IRR that returns to Grade 1 in less than 6 hours
Hematologic

 • ≥ Grade 3 thrombocytopenia with clinically significant bleeding (requires hospitalization, transfusion of blood products, or other urgent medical intervention). • Grade 4 neutropenia or thrombocytopenia lasting > 7 days. • ≥ Grade 3 febrile neutropenia (ANC < 1.0 × 10⁹/L and fever > 101°F/38.3°C). • Grade 4 (life-threatening) anemia not explained by underlying disease.
General

 • Subjects being unable to receive ≥ 75% of study drug doses during the DLT observation period because of toxicity, even if the toxicity does not meet DLT criteria defined above. Note: Exceptions include the DLT exclusions mentioned above. • Any death not clearly due to the underlying disease or extraneous causes.

Note: Transient (≤ 72 hours) abnormal laboratory values without associated clinically significant signs or symptoms based on investigator determination will not be considered a DLT.

^a Hy's law is defined as 1) ALT or AST elevation > 3 times ULN AND 2) total bilirubin > 2 times ULN, without initial findings of cholestasis (elevated serum alkaline phosphatase), AND 3) no other apparent possible causes of aminotransferase elevation and hyperbilirubinemia, including, but not limited to, viral hepatitis, pre-existing chronic or acute liver disease, or the administration of other drug(s) known to be hepatotoxic.

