4.1.1. Phase 1 – Dose Escalation

Dose escalation in Treatment Groups A and B will be conducted using a standard 3 + 3 + 3 design as per the dose-escalation schedule outlined in Table 3. A minimum of 3 evaluable subjects will be enrolled in each treatment group beginning with Dose Level 1 (starting dose of epacadostat 50 mg BID in Treatment Groups A and B).

In Treatment Group A, the first 3 evaluable subjects at each dose level will be observed for a minimum of 42 days before the next dose level begins enrollment. To be evaluable for tolerability, subjects must receive at least 75% of planned epacadostat doses (63/84) at the specified dose level, 3 doses of nivolumab, and 1 dose of ipilimumab, or subjects must experience a DLT during the DLT observation period.

In Treatment Group B, the first 3 evaluable subjects at each dose level will be observed for a minimum of 42 days before the next dose level begins enrollment. To be evaluable for tolerability, subjects must receive at least 75% of planned epacadostat doses (63/84) at the specified dose level, 3 doses of nivolumab, and 2 doses of lirilumab, or subjects must experience a DLT during the DLT observation period.

Subjects who discontinue for reasons other than a DLT (eg, events clearly associated with the underlying disease, disease progression, concomitant medication, comorbidity, or an AE clearly

unrelated to study treatment) during a DLT observation period will be considered nonevaluable for DLT evaluation and will be replaced.

Alternate doses or dose administration schedules, including sequenced (rather than concurrent) administration of treatment components, [REDACTED] and safety results.

For both treatment groups, the following dose-escalation rules apply:

- If 0 of the first 3 evaluable subjects at a dose level have a DLT, 3 subjects will be enrolled and treated at the next higher dose level (if applicable).
- If 1 of the first 3 evaluable subjects at a dose level has a DLT, that dose level will be expanded to 6 subjects. If ≤ 1 of 6 subjects in a dose level has a DLT, 3 subjects will be enrolled and treated at the next higher dose level (if applicable).
- If 2 of 6 subjects at a dose level have a DLT, that dose level will be expanded to include 9 subjects.
- If ≥ 2 of 3, ≥ 3 of 6, or ≥ 3 of 9 subjects have DLTs at a specific dose level, that dose level will be determined to have exceeded the MTD, and the previous dose level will be considered the MTD.

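### In Group A, a reversible Grade 3 irAE that cuts dosing can leave a subject neither a DLT nor evaluable, so the reported DLT denominator can depend on drug toxicity

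*Combined protocol and SAP*

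**What the plan says.** Four rules act together.

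- **The exemption.** Section 5.4.2 says that a Grade 3 irAE returning to Grade 1 or lower "within 14 days after the initiation of supportive care or corticosteroid therapy may be deemed a non-DLT". Table 7 repeats it, listing among the exceptions to the Grade 3 nonhematologic DLT a "Grade 3 irAE that improves to ≤ Grade 1 in ≤ 14 days by appropriate care or with corticosteroid therapy".
- **The missed-dose DLT and its Note.** The General row of Table 7 makes this a DLT: "Subjects being unable to receive ≥ 75% of study drug doses during the DLT observation period because of toxicity", whether or not the toxicity is a DLT in its own right. The Note to that row then says: "Exceptions include the DLT exclusions mentioned above".
- **Evaluability.** Unless they have a DLT, Group A subjects "must receive at least 75% of planned epacadostat doses (63/84) at the specified dose level, 3 doses of nivolumab, and 1 dose of ipilimumab" to be evaluable for tolerability.
- **Replacement.** Under Section 4.1.1, subjects who discontinue for reasons other than a DLT "during a DLT observation period will be considered nonevaluable for DLT evaluation and will be replaced". Under Section 4.3.2, a Phase 1 subject "who does not have the required exposure to the study drugs during the DLT evaluation period, may be replaced".

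The toxicity guidance decides how much dosing is lost. Section 5.4.4 says that an interruption should cover all components. Tables 9 and 10 restart epacadostat one level lower after a Grade 3 event. Tables 11, 12, 13 and 15 advise stopping treatment for Grade 3 pneumonitis, enterocolitis, hepatitis and neuropathy, with exceptions through the medical monitor. Tables 14 and 16 allow a same-dose restart for dermatitis and endocrinopathy.

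**The concern.** The missed-dose row of Table 7 is the rule that should catch a subject who could not stay on treatment because of the drugs. For a reversible Grade 3 irAE, its Note turns that rule off. The subject then has no DLT, may fail the exposure rule because of the toxicity, and may be replaced by someone else. Whether a subject stays in the DLT-evaluable set would then depend on drug toxicity, so the missingness is informative. The examples in Section 4.1.1 (progression, comorbidity, clearly unrelated AEs) suggest that replacement was meant for losses unrelated to the drugs.

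DLTs and the MTD or PAD are the Phase 1 primary objective (Table 2). If the Group A report gives DLTs/n by dose level, a reader could not tell whether a treatment-limiting irAE stands behind a replaced subject. Section 9.4.2.5 counts irAEs that led to interruption, reduction or discontinuation, but not by DLT status or evaluability. The legible text of Section 9 defines safety, full analysis and per-protocol sets, and no DLT-evaluable set.

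**Working it through.** **Inputs.** DLT window of 42 days (5.4.2); epacadostat twice daily (5.2.1); threshold 63/84 at the specified level (5.4.2); nivolumab on Day 1 of each 14-day cycle (5.2.2.1).

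**The plan's own figure.** 42 × 2 = 84 planned doses; 0.75 × 84 = 63. This reproduces exactly. Doses that may be missed: 84 − 63 = 21, or 21 / 2 = 10.5 days.

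**Route 1, hold with same-dose restart.** Doses left after a hold of h days inside the window = 84 − 2h.

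| Hold | Doses | Share | Meets 63/84 |
|---|---|---|---|
| 10 days | 64 | 76.2% | yes |
| 11 days | 62 | 73.8% | no |
| 14 days | 56 | 66.7% | no |

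A hold of 11 to 14 days can therefore fail the exposure rule while the event still qualifies for the 14-day exemption.

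**Route 2, restart one level lower.** Only doses before onset count at the specified level. For onset on Day d, that is 2(d − 1). Day 32 gives 62 (fails) and Day 33 gives 64 (passes). With onset through about Day 32, even a short hold is enough.

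**Route 3, permanent stop.** A last dosing day of Day 31 gives 62/84 = 73.8% (fails); Day 32 gives 64/84 = 76.2% (passes). Stopping before the third nivolumab dose also fails. That dose falls nominally on Day 29, but visits have a ±3-day window, so it could be given as early as Day 26. No firm cut-off should be drawn from nivolumab.

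**Direction of the effect.** Let p be the rate of other DLTs and q the rate of exempt events that make the subject nonevaluable.

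- Subject dropped and replaced: p / (1 − q)
- Subject kept as a non-DLT: p
- Subject kept as a DLT: p + q

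For positive p and q with p + q < 1, the dropped-subject rate lies between the other two. The documents give neither p nor q. Assuming p = 0.20:

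| q (assumed) | Non-DLT | Dropped | DLT |
|---|---|---|---|
| 0.05 | 0.20 | 0.211 | 0.25 |
| 0.10 | 0.20 | 0.222 | 0.30 |
| 0.20 | 0.20 | 0.250 | 0.40 |

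**One dose level, for illustration.** Six evaluable subjects without a DLT, plus one replaced subject, with 95% exact binomial intervals:

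- As called: 0/6, interval 0–46% (upper limit 1 − 0.025^(1/6) = 0.459)
- Restored as a non-DLT: 0/7, interval 0–41% (upper limit 1 − 0.025^(1/7) = 0.410)
- Restored as a DLT: 1/7 = 14%, interval 0.4–58%

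**The case against.** The exemption is a deliberate and defensible choice. Under the protocol's own definition the lost subject is a non-DLT, and removing a non-DLT shrinks only the denominator, which raises the observed rate. A reader might infer that the rule simply biases the DLT rate downward. The documents do not support that: it holds only against a standard that counts the event as dose-limiting. This objection stands, and it is why the supportive analysis should be shown both ways.

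The loss is also not mechanical. The exemption is permissive, sponsor and investigators jointly adjudicate high-grade AEs (5.4.3), the medical monitor can allow exceptions to stopping, and the hepatic algorithm in Appendix B allows delay for some cases. Grade 4 irAEs, Hy's law cases and ocular irAEs of Grade 2 or higher remain DLTs. A dose with only 3 evaluable subjects needs at least 3 more before it becomes the RP2D (4.1.1), and later toxicity can lower the MTD (5.4.2). All of this stands.

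The events remain in the safety population (9.1), the AE listings (9.4.2.1) and the irAE summary. Section 9 also refers to a separate Statistical Analysis Plan for some details, and part of the text is redacted, so a DLT-evaluable set may be defined elsewhere. What the legible text lacks is a link between these events and DLT status or replacement.

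Two further inferences should be resisted. One is that an escalation decision is at risk, since a single event separates 0/3 from 1/3. Amendment 2 closed enrollment, so no decision remains to change. The other is that the irAE exception also rescues a Grade 3 rash treated with systemic steroids. Table 7 has its own rash exclusion, for "Grade 3 rash in the absence of desquamation, with no mucosal involvement, that does not require systemic steroids", and the specific rule reasonably controls.

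**Conclusion.** The gap is real on the text and limited in reach. In Group A, a subject whose dosing is stopped, held for 11 or more days, or reduced one level with onset through about Day 32 because of an exempt Grade 3 irAE can have no DLT, fail the exposure rule at 62/84 doses or fewer, and be replaced. Replacement can therefore depend on drug toxicity, and the DLT denominator becomes informative.

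Per event, the effect on a report is of the order of 0/6 against 0/7 or 1/7. Toxicity is understated relative to counting the event as dose-limiting; relative to counting it as a non-DLT, only the denominator shrinks. The conclusion assumes that the Note to the General row means what it says and that DLTs/n or an MTD/PAD statement will be reported for Group A. The documents do not say whether any such event occurred. No subjects entered Group B, so nothing follows there. This is a cheap improvement to reporting, not a flaw that invalidates Phase 1.

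**What to change.** Keep the DLT calls made during the study as the main result. Then add two items to the selected safety analyses allowed by Section 9.4.

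1. **A listing** of every Group A Phase 1 subject called nonevaluable or replaced after a treatment-related event in Days 1–42. Give the event, grade, onset day, days to Grade 1 or lower, doses received at the assigned level, and replacement status.
2. **A supportive DLTs/n by dose level** that keeps these subjects in the denominator, counted once as non-DLT and once as DLT (0/7 and 1/7 beside 0/6 in the example).

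If there were no such subjects, one sentence saying so is enough.

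If the wording is amended or reused in another protocol, limit the Note to the General row so that failing the exposure rule because of a Grade 3 irAE cannot make a subject nonevaluable and replaceable.

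The cost is one small table and one listing, with no new subjects or visits. The data are already collected: Section 8.1.2 records each change of grade with its dates, and Section 5.3 covers tablet counts and infusions. The downside is a possibly higher supportive DLT rate printed beside the main result.
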